### **5.2.2 Definition of Dose-Limiting Toxicities**

All toxicities will be graded using NCI CTCAE Version 4.0 based on Investigator assessment (Appendix 12.5).

The DLT window of observation will be during Cycle 1 (Day 1 to Day 21).

The occurrence of any of the following toxicities during Cycle 1 will be considered a DLT, if assessed by the Investigator to be possibly, probably or definitely related to study drug administration:

- 1) Grade 4 non-hematologic toxicity (not laboratory).
- 2) Grade 4 hematologic toxicity lasting  $\geq 7$  days, except thrombocytopenia
  - a) Grade 4 thrombocytopenia of any duration
  - b) Grade 3 thrombocytopenia associated with bleeding
- 3) Grade 3 non-hematologic toxicity (not laboratory) lasting  $>3$  days despite optimal supportive care.

- 4) Any Grade 3 or Grade 4 non-hematologic laboratory value if:
  - Medical intervention is required to treat the subject, or
  - The abnormality leads to hospitalization, or
  - The abnormality persists for >72 hours.
  - Exceptions:
    - Clinically non-significant, treatable, or reversible laboratory abnormalities including uric acid, etc.
- 5) Any of the following liver test abnormalities are observed (Hy's Law)
  - ALT or AST > 3X ULN **with** TBL > 2X ULN with no elevation in alkaline phosphatase (AP < 2X ULN)
  - No other reasons can be found to explain the combination of increased AT and TBL, such as viral hepatitis, A,B or C, preexisting or acute liver diseases, or another drug capable of causing the observed injury
- 6) Febrile neutropenia Grade 3 or Grade 4:
  - Grade 3 is defined as ANC <1000/mm^3 with a single temperature of >38.3 degrees C (101 degrees F) or a sustained temperature of ≥38 degrees C (100.4 degrees F) for more than one hour
  - Grade 4 is defined as ANC <1000/mm^3 with a single temperature of >38.3 degrees C (101 degrees F) or a sustained temperature of ≥38 degrees C (100.4 degrees F) for more than one hour, with life-threatening consequences and urgent intervention indicated.
- 7) Prolonged delay (>2 weeks) in initiating cycle 2 due to treatment-related toxicity.
- 8) Any treatment-related toxicity which causes the subject to discontinue treatment during Cycle 1.
- 9) Missing >25% of Preladenant doses as a result of drug-related AE(s) during the first cycle.
- 10) Grade 5 toxicity.

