6.1	Flow Chart	Vital sign measurements were added to cycle 1 day 8 visit for both preladenant monotherapy arm and in combination with pembrolizumab arm.	This change was made at the request of the FDA as an extra safety precaution.
5.1.2	Subject Inclusion Criteria (Table 2)	The protocol was clarified in Coagulation section for INR and PT values when patients are using anticoagulant therapy.	This change was made at the request of FDA for clarification.
5.2.3.2	Table 8	Delete language “Appropriate resuscitation equipment should be available in the room and a physician readily available during the period of drug administration.” Since it is no longer applicable in current study.	The language is not applicable in this study.

Section Number (s)	Section Title(s)	Description of Change (s)	Rationale
5.2.2	Definition of Dose-Limiting Toxicities	The duration of any Grade 3 or Grade 4 non-hematologic laboratory value was changed from 1 week to 72 hours.	This change was made at the request of the FDA as an extra safety precaution.
5.2.2	Definition of Dose-Limiting Toxicities	Liver function test was eliminated from the exceptions for any Grade 3 or Grade 4 non-hematologic laboratory value.	This change was made at the request of the FDA as an extra safety precaution.
5.2.2	Definition of Dose-Limiting Toxicities	Liver test abnormalities (Hy's Law) was added to the definition of DLT.	This change was made at the request of the FDA as an extra safety precaution.
5.5.2.2	Prohibited Concomitant Medications for Pembrolizumab	Protocol was clarified for glucocorticoids dose limit and conditions for pembrolizumab prohibited medication.	This change was made at the request of FDA for clarification.

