### **5.2.2.1 Replacement of Subjects in DLT Period**

In order to fully evaluate the safety of the combination therapy in this study, all subjects enrolled must meet the criteria for evaluability for Cycle 1. Subjects are considered non-evaluable and will be replaced if:

- They are enrolled but not treated,
- They discontinue from the trial prior to completing all safety evaluations due to reasons other than drug-related AEs,
- They received <90% of the total pembrolizumab infusion in Cycle 1 (e.g., because the infusion had to be discontinued due to an infusion reaction) and did not experience a drug-related event,
- They received  $\leq 75\%$  of preladenant doses intended for the trial during Cycle 1 and did not experience a drug-related AE,
- They must take a prohibited concomitant medication during Cycle 1, unless this medication is used to treat a study drug-related AE,
- They must undergo medical / surgical procedures or have logistical issues not related to study therapy (e.g., elective surgery, unrelated medical events) during Cycle 1.

Non-evaluable subjects will not be counted toward the cohort total for DLT evaluation.

Subjects who experience a DLT in Cycle 1 should be discontinued from treatment. However, if in the opinion of the Investigator, the subject is deriving clinical benefit from the study treatment, the subject may be allowed to continue on the study upon resolution of the DLT to a  $\leq$  Grade 1 adverse event and after discussion with the sponsor.

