
 
Any Grade 3 or 4 non-hematological toxicity (not including laboratory, unless clinically significant medical intervention is required to treat the subject, or the abnormality leads to hospitalization, or the abnormality persists for >1 week)
 
	Yes	Treatment may be restarted when AE resolves back to baseline or to Grade 1.	Decrease dose by one dose level.	If AE persists for 12 weeks without resolution following reduction in dose. Permanent discontinuation should be considered for any severe or life-threatening event

In case toxicity does not resolve to Grade 0-1 within 12 weeks after last treatment, preladenant should be discontinued after consultation with the Sponsor.

With Investigator and Sponsor agreement, subjects with a laboratory adverse event still at Grade 2 after 12 weeks may continue treatment in the trial only if asymptomatic and controlled.

After any Grade 4 drug-related adverse event, subjects should not restart study treatment without consultation with the Sponsor. (Toxicity must have resolved to 0-1 or baseline prior to restarting).

Dose reductions are not permitted during Cycle 1.

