20. Urine dipstick or microscopic urinalysis may be performed according to site SOP. Urine dipstick includes pH, protein, glucose, leukocyte-esterase, ketones, and nitrite. Mandatory microscopic urinalysis will be performed if the dipstick results are abnormal. Microscopic analysis includes white blood cell count, red blood cell count, epithelial cells and casts.
21. Serum Chemistry tests include sodium, potassium, calcium, phosphate, chloride, bicarbonate/CO2 (if performed in region), BUN or Urea, creatinine (Cystatin C if abnormal), SGOT (AST), SGPT (ALT), total proteins, total bilirubin (direct bilirubin if abnormal), albumin, alkaline phosphatase, glucose, uric acid, amylase, lipase, Lactate Dehydrogenase (LDH) and  $\gamma$ -glutamyltransferase (GGT). Serum chemistry does not need to be repeated on C1D1 if screening samples were obtained within 3 days of C1D1.
22. Coagulation factors (PT/INR and aPTT) should be tested as part of the screening procedures for all subjects. Furthermore, any subject receiving anticoagulant therapy should have coagulation factors monitored closely throughout the trial.
23. For women of reproductive potential, a urine pregnancy test will be performed at Screening and within 72 hours prior to the first dose of study treatment. If a urine pregnancy test cannot be confirmed as negative, a serum pregnancy test is required and should be negative. Additional pregnancy testing should be conducted as per local regulations where applicable.
24. On-treatment tumor biopsy will be performed on Day 15 of Cycle 2 (+/- 7 Days). Tumor tissue will be sent to designated laboratory for biomarker analysis and leftover tissue may be saved for future biomedical research if the subject signs the FBR consent.
25. Procedures for collection of PK samples and precise time points are described in the Procedures Manual. Samples for preladenant and its metabolites pharmacokinetic (PK) testing should be collected prior to dosing, and 1 hour, 2 hours, 4 hours and 8 hours after drug administration of preladenant (+/- 10 minutes) on Cycle 1 Day 1 and Cycle 2 Day 1; Prior to dosing on Cycle 1 Day 8; Prior to dosing on Cycle 1 Day 15; Prior to dosing on Cycle 4 Day 1; And, Prior to dosing on Cycle 8 Day 1. If the sample day falls on a weekend or a holiday, please consult the Sponsor for alternate sample collection times.

Preladenant in Combination with Pembrolizumab (Arm 2 ; Part 1 and Part 2) and (cross-over subjects)												

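### The laboratory exception in DLT criterion 4 can cancel the criterion's own 72-hour trigger, mainly for an isolated ALT or AST rise in Arm 1 that recovers within a week

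*Combined protocol and SAP*

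**What the plan says.** Section 5.2.2, criterion 4, applies to Grade 3 or 4 non-hematologic laboratory values in Cycle 1 that the investigator relates to study drug. It has three triggers. The first is "Medical intervention is required to treat the subject, or", the second is hospitalization, and the third is "The abnormality persists for >72 hours". An exceptions line follows: "Clinically non-significant, treatable, or reversible laboratory abnormalities including uric acid, etc".

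Other rules bear on the same events:

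- **Criterion 5** (Hy's Law) needs bilirubin above 2 times ULN together with ALT or AST above 3 times ULN.
- **Criteria 7 and 8** cover a delay of more than 2 weeks in starting Cycle 2, and discontinuation during Cycle 1.
- **Criterion 9** is "Missing >25% of Preladenant doses as a result of drug-related AE(s) during the first cycle".
- **Table 7** (Section 5.2.3.1) requires a preladenant hold for Grade 3-4 non-hematologic toxicity, "not including laboratory, unless clinically significant medical intervention is required to treat the subject, or the abnormality leads to hospitalization", or the abnormality lasts more than 1 week. Restart is one dose level lower, and dose reductions are barred in Cycle 1.
- **Table 8** (Section 5.2.3.2) requires permanent pembrolizumab discontinuation for Grade 3 or higher AST, ALT or bilirubin (with a liver-metastasis exception), for Grade 3-4 renal failure or nephritis, and for other Grade 4 drug-related toxicity.

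The Summary of Changes records the sponsor's intent: "Liver function test was eliminated from the exceptions for any Grade 3 or Grade 4 non-hematologic laboratory value". The same amendment shortened the duration trigger from 1 week to 72 hours. Both changes were made at FDA request.

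**The concern.** The three descriptors in the exception are joined by *or*, so *reversible* is a ground for exemption beside clinical non-significance. It carries no time limit. A value that stayed at Grade 3 beyond 72 hours and then recovered satisfies both the trigger and the exception, and the exception wins. The open-ended *etc.* leaves the analytes undefined, and no adjudication is described, so two investigators could classify the same event differently.

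The pattern most likely to fall here is one the protocol already associates with this drug. Section 4.1.3.1 names liver enzyme increases as a preladenant risk. It reports that subjects with ALT elevations in the later trials had no clinically meaningful concurrent rise in other liver tests, and that no subject met Hy's Law. Criterion 5 would miss such a rise, which leaves criterion 4 as the direct rule.

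The DLT rate is the primary safety endpoint (Section 8.4.2), and DLT counts drive the Table 4 decisions (Section 5.2.1.2). An exempted event is missing from both. It also does not bring in the rule that "Subjects who experience a DLT in Cycle 1 should be discontinued from treatment" (Section 5.2.2.1).

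**Working it through.** **1. Threshold for criterion 9.** Preladenant is given twice daily for 21 days, so Cycle 1 has 21 × 2 = 42 doses. A quarter is 10.5, so at least 11 missed doses (11/42 = 26.2%) are needed.

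| Hold | Doses missed | Share of 42 | Criterion 9 |
|---|---|---|---|
| Day 16 morning to Day 21 | 12 | 28.6% | met |
| Day 16 evening to Day 21 | 11 | 26.2% | met |
| Day 17 morning to Day 21 | 10 | 23.8% | not met |
| Any 5 full days | 10 | 23.8% | not met |

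**2. Events that are caught.** Clinically significant intervention or hospitalization forces a Table 7 hold. Restart requires a lower dose, which Cycle 1 does not allow, so the hold runs to Day 21. If it starts by Day 16, criterion 9 makes the event a DLT whatever criterion 4's exception says. An abnormality lasting more than 1 week is caught the same way if it began by about Day 9 (9 + 7 = 16).

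**3. The Arm 1 gap.** Take a related, isolated Grade 3 ALT that lasts 4 to 5 days, without intervention or hospitalization, and recovers.

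- Criterion 4: the 72-hour trigger is met, but the value can be exempted as reversible.
- Criterion 5: not met, because bilirubin has not risen.
- Table 7: no forced hold, because its persistence limit is 1 week.
- Criteria 7 and 8: need not apply.
- Criterion 9: not met, even with a voluntary 5-day hold (10 of 42 doses).

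**4. Late onset.** A hold for intervention or hospitalization that starts after Day 16, or an abnormality that starts after about Day 9 and lasts more than 1 week, misses too few Cycle 1 doses for criterion 9. Such an event counts only if another criterion applies, for example a Cycle 2 delay of more than 2 weeks.

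**5. Arm 2.** Section 2.1 lists pembrolizumab alone as continued Arm 2 treatment but not preladenant alone. A discontinuation required by Table 8 therefore points to criterion 8. What remains exposed is some Grade 3 values outside the liver and renal rows, and liver values under the liver-metastasis exception.

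**6. Sensitivity of Table 4.** Inputs from the table footnote: Beta(1,1) prior, target 0.30, ε = 0.03. With x DLTs in n subjects the posterior is Beta(1+x, 1+n−x), with distribution function F. The unit probability masses are F(0.27)/0.27 for E, [F(0.33) − F(0.27)]/0.06 for S and [1 − F(0.33)]/0.67 for D; the largest decides. DU applies if 1 − F(0.30) > 0.95. The 0.95 cutoff is an assumption, as the protocol does not state it.

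This reproduces all 78 printed cells in rows 0 to 6. Rows 7 and 8 are broken in the available text and were taken from the recomputation.

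Steps from x to x−1 that change the decision:

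| n | 3 | 4 | 5 | 6 | 7 | 8 | 9 | 10 | 11 | 12 | 13 | 14 |
|---|---|---|---|---|---|---|---|---|---|---|---|---|
| changes | 3 | 2 | 3 | 2 | 3 | 3 | 2 | 3 | 2 | 3 | 2 | 3 |

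- n = 3 to 6: 3 + 2 + 3 + 2 = 10 of 3 + 4 + 5 + 6 = 18 steps.
- n = 3 to 14: 31 of 102 steps (30.4%).

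For example, 1/3 Stay becomes 0/3 Escalate, and 4/6 DU becomes 3/6 Stay. Some changes are only DU to D, and both of those de-escalate: 3/3 and 4/5 for n = 3 to 6, and one each at n = 3, 5, 7, 8, 10, 12 and 14 overall. Without them the counts are 10 − 2 = 8 of 18 and 31 − 7 = 24 of 102 (23.5%).

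**The case against.** A reader might infer that any treated or hospitalized laboratory abnormality escapes the DLT count. The documents do not support that, because step 2 catches those events when the hold starts by Day 16. Section 5.2.3.1 allows departures from Table 7 only in exceptional circumstances after Sponsor consultation. Arm 2 is also well covered, since Section 7.2.4 assigns causality to the combination by default and Table 8 then applies. This part of the objection stands and sets the scope of the point.

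A reader might also infer that the liver-test change was not carried out. It was: liver tests are no longer named in the exception, and no mismatch with the change log is alleged. One can argue further that clinical non-significance governs the whole list, or that *uric acid, etc.* limits it to minor changes. Either reading is possible and fits the sponsor's intent better. Neither is what the words say, and if only non-significant values were meant, the other two descriptors would be unnecessary.

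Scheduled Cycle 1 chemistry falls on Days 1, 8 and 15 (Section 6.1), so showing a 4 to 5 day duration normally takes an unscheduled test, which Section 7.1 permits. An untreated value that recovers might also be excepted as clinically non-significant, a ground the fix keeps. That is why the fix makes the liver tests ineligible by name.

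Finally, exempted events stay in the adverse event and laboratory summaries (Section 8.6.2) and in the safety review before the next dose level (Section 5.2.1.4). The RP2D rests on the totality of the data (Section 5.2.1.2). These safeguards limit the harm, but they do not put the event back into the primary endpoint or Table 4.

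**Conclusion.** The point holds in a limited form. As worded, the exception can cancel the 72-hour trigger. The main exposure is an Arm 1 laboratory value, notably an isolated Grade 3-4 ALT or AST, lasting more than 72 hours but not more than 1 week without clinically significant intervention or hospitalization. The late-onset and residual Arm 2 cases in steps 4 and 5 are secondary.

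The figures of 10 of 18 and 31 of 102 weight every step equally and describe the effect of any single reclassified event. The documents give no frequency for Grade 3-4 values of this duration; the liver data in Section 4.1.3.1 use a threshold of 3 times ULN. It would be tempting to infer a shift in escalation probability, but that needs an assumed share of exempted DLTs for which the documents offer no basis, so none is claimed.

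The conclusion rests on reading the exception literally and, for the Table 4 counts, on the assumed 0.95 cutoff. This is a cheap improvement to the wording, not a flaw in the dose-finding design.

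**What to change.** In criterion 4 of Section 5.2.2:

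- delete *treatable, or reversible* and *etc.*;
- limit the exception to clinically non-significant abnormalities in analytes the sponsor names, such as uric acid and any promptly corrected electrolytes;
- state that Grade 3-4 ALT, AST and bilirubin are not eligible for the exception.

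The cost is a wording change in the protocol, with no new procedures or subjects. The downside is that a few more events may count as DLTs, which could hold escalation at a lower dose. The documents give no frequency from which to size this. Naming promptly corrected electrolytes in the exception keeps it small.

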### **5.2.1.2 Dose Escalation and Confirmation**

In Part 1 of the study, an mTPI design [1] with a target DLT rate of approximately 30% will be applied for dose escalation and confirmation to determine a RP2D in each treatment arm (preladenant monotherapy [Arm 1] and preladenant in combination with pembrolizumab [Arm 2]). The final number of subjects enrolled in Part 1 will depend on the empirical safety observations (DLT occurrence), and what dose is ultimately identified as the RP2D using the mTPI design.

Four pre-determined dose levels of preladenant in each arm will be explored independently in Part 1: 25 mg BID, 50 mg BID, 100 mg BID, and 200 mg BID. A 10 mg BID de-escalation dose (DL-1) will be used as an alternative dose level should 25 mg BID prove to be intolerable. Lower and/or higher doses of preladenant may be explored depending on the combined safety, PK/PD data available at each dose level. All dose escalation and de-escalation decisions will be based on the occurrence of DLTs at a given dose and will be made jointly by the investigators and the Sponsor. In Arm 2, the dose of pembrolizumab will remain constant at 200 mg every 3 weeks in Part 1 and Part 2 of the study.

Treatment allocation will be accomplished by non-random assignment. Enrollment in Arm 1 (preladenant in monotherapy) at DL2 will begin once all subjects complete Cycle 1 at DL1 of Arm 1 and a dose escalation decision has been made. Enrollment in Arm 2 (preladenant in combination with pembrolizumab) at DL1 will also begin once all subjects complete Cycle 1 at DL1 of Arm 1 and a dose escalation decision has been made. Thus, the starting dose of preladenant in the combination arm will generally be 1 dose level below the dose being tested concurrently in the preladenant monotherapy arm.

When both treatment arms are open for enrollment, IVRS/IWRS will alternate subject assignment between Arm 1 and Arm 2 starting with Arm 1. For example, once the 50 mg BID dose cohort of Arm 1 (preladenant monotherapy) and the 25 mg BID dose cohort of Arm 2 (preladenant in combination with pembrolizumab) are open for enrollment, the first subject will be allocated to Arm 1, the second subject will be allocated to Arm 2, the third subject will be allocated to Arm 1, etc. Each new dose cohort will open for enrollment

without delay once the 21 day DLT observation period of the previous dose cohort is completed and a dose escalation decision is made.

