#### **5.2.3.1 Preladenant Dose Modifications**

Adverse events (both non-serious and serious) associated with preladenant and pembrolizumab exposure may represent an immunologic etiology. These adverse events may occur shortly after the first dose or several months after the last dose of treatment.

The Common Terminology Criteria for Adverse Events, version 4.0 (CTCAE 4.0) must be used to grade the severity of adverse events. The investigator may attribute each toxicity event to preladenant alone, or to the combination of preladenant and pembrolizumab, and modify the dose according to [Table 7](#) and [Table 8](#) (*pembro dose mod table added to Section 5.2.3.2*). If a dose modification for toxicity occurs with preladenant, the dose may not be re-escalated to the dose which preceded the dose modification. Dose modifications are always based on the previous cycle.

Reduction or holding of one agent and not the other agent is appropriate if, in the opinion of the investigator, the toxicity is clearly related to one of the study drugs. For example, in the combination arm (Arm 2), if preladenant is held due to an adverse event attributed to that drug, then pembrolizumab may continue to be administered. Appropriate documentation is required regarding which drug the investigator is attributing the adverse event to. If, in the opinion of the investigator, the toxicity is related to the combination of two agents, then both drugs should be held according to recommended dose modifications.

Subjects may have up to 2 dose modifications of preladenant throughout the course of the study, as described in Table 7. If further toxicity occurs or the criteria for resuming treatment are not met, the subject must be discontinued from the agent. If a subject experiences several toxicities and there are conflicting recommendations, follow the most conservative dose adjustment recommended (dose reduction appropriate to the most severe toxicity).

Exceptional circumstances to following the dose modification tables below may be considered after consultation with the Sponsor.

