**Table 7 Preladenant Dose Modification and Treatment Discontinuation Guidelines for Drug-Related Adverse Events**

Toxicity	Hold Treatment	Criteria for Restarting Treatment	Dose/Schedule for Restarting Treatment	Criteria for Discontinuation after Consultation with Sponsor
Hematological toxicities:				
• Any Grade 1 hematological toxicity	No	N/A	N/A	N/A
• Any Grade 2 hematological toxicity, or Grade 3 toxicity that persists for ≤ 5 days	Per medical assessment of the Investigator	If treatment held, may be restarted when AE resolves back to baseline or to Grade 1.	Per medical assessment of the investigator: may decrease dose by one dose level.	If AE persists for 12 weeks without resolution following reduction in dose.
• Any Grade 3 hematologic toxicity that persists for > 5 days, or Grade 4 hematological toxicity • Febrile neutropenia • Grade 3 thrombocytopenia of any durations if associated with bleeding	Yes	Treatment may be restarted when AE resolves back to baseline or to Grade 1.	Decrease dose by one dose level.	If AE persists for 12 weeks without resolution following reduction in dosing schedule.  Permanent discontinuation should be considered for any severe or life-threatening event
Non-hematological toxicities:				
• Toxicity	Hold Treatment	Criteria for Restarting Treatment	Dose/Schedule for Restarting Treatment	Criteria for Discontinuation after Consultation with Sponsor
• Any Grade 1 non-hematological toxicity • Grade 2 alopecia • Grade 2 fatigue	No	N/A	N/A	N/A
• Any Grade 2 non-hematological toxicity except Grade 2 alopecia and Grade 2 fatigue	Per medical assessment of the investigator	If treatment held, may be restarted when AE resolves back to baseline or to Grade 1.	Per medical assessment of the Investigator: may decrease dose by one dose level.	If AE persists for 12 weeks without resolution following reduction in dose.

Toxicity	Hold Treatment	Criteria for Restarting Treatment	Dose/Schedule for Restarting Treatment	Criteria for Discontinuation after Consultation with Sponsor

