### 5.2.3.2 Pembrolizumab Withholding

AEs (both non-serious and serious) associated with pembrolizumab exposure may represent an immunologic etiology. These AEs may occur shortly after the first dose or several months after the last dose of treatment. Pembrolizumab must be withheld for drug-related toxicities and severe or life-threatening AEs as per [Table 8](#). Pembrolizumab dose reductions are not permitted during the trial.

In addition, subjects should receive appropriate supportive care measures as deemed necessary by the treating investigator. Suggested supportive care measures, as described in Section 5.6.2, are also included in ([Table 8](#)).

Dosing interruptions are permitted after Cycle 1 in the case of medical/surgical events or logistical reasons not related to trial therapy (e.g., elective surgery, unrelated medical events, subject vacation, and/or holidays). Subjects should be placed back on trial therapy within 3 weeks of the scheduled interruption, unless otherwise discussed with the Sponsor. The reason for interruption should be documented in the subject's trial record.

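### One listed DLT (Cycle 2 delayed by more than two weeks) cannot be known when the Day 1–21 window closes, and late-onset duration criteria may still be open; no rule scores such a subject or makes a dose decision wait

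*Combined protocol and SAP*

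**What the plan says.** Section 5.2.2 sets the window: "The DLT window of observation will be during Cycle 1 (Day 1 to Day 21". It then counts a listed toxicity as a DLT if it occurs in Cycle 1 and is judged related. Of the ten criteria, these matter here:

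- Criterion 7: "Prolonged delay (>2 weeks) in initiating cycle 2 due to treatment-related toxicity".
- Three criteria that depend on duration: Grade 4 hematologic toxicity for at least 7 days (thrombocytopenia has its own rule), Grade 3 non-hematologic toxicity for more than 3 days, and Grade 3–4 non-hematologic laboratory values for more than 72 hours. A laboratory value also qualifies at once if it needs medical intervention or leads to hospitalization.
- Criterion 9: "Missing >25% of Preladenant doses as a result of drug-related AE(s) during the first cycle".

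On timing, section 5.2.1.2 opens each new cohort "without delay once the 21 day DLT observation period of the previous dose cohort is completed and a dose escalation decision is made", and section 5.3 repeats this. Section 5.2.1.4 leaves the decision to the sponsor, consulting the investigators after a safety review. At DL1, one Arm 1 decision opens both Arm 1 at 50 mg BID and Arm 2 at 25 mg BID with pembrolizumab. Section 8.5.1 makes a subject evaluable for DLT after 21 days of observation, or on an earlier DLT. Sections 5.2.2.1 and 5.9 define only non-evaluable subjects and their replacement.

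Table 7 requires preladenant to be held for "Any Grade 3 hematologic toxicity that persists for > 5 days, or Grade 4 hematological toxicity" and for "Any Grade 3 or 4 non-hematological toxicity (not including laboratory, unless clinically significant medical intervention is required to treat the subject", with further laboratory conditions.

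**The concern.** The mTPI rule acts on one number, the count of subjects with a DLT among those treated at the dose. Section 5.2.2 defines some DLTs that cannot be settled by Day 21, while the operational sections allow that count to be used from Day 21. A subject whose status is still open would then be read by default as having no DLT.

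The people exposed are those enrolled at the next dose, or added at the current dose, on the strength of that reading. There is a second effect on the primary endpoint, the DLT rate. A subject who completes 21 days enters the denominator under section 8.5.1, but nothing says whether a criterion 7 event confirmed later enters the numerator.

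**Working it through.** **1. Table 4 reproduces.** Inputs from the table footnote: target 0.30, ε1 = ε2 = 0.03, prior Beta(1,1). With x DLTs in n subjects the posterior is Beta(1+x, 1+n−x). Take the largest of P(p<0.27)/0.27 (E), P(0.27≤p≤0.33)/0.06 (S) and P(p>0.33)/0.67 (D), with DU if P(p>0.30) > 0.95. The 0.95 cutoff is an assumption; the documents do not state it. Rows 0 to 6 match cell for cell. The table is sound, so the question is only about the count fed into it.

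**2. Criterion 7.** A 21-day cycle puts Cycle 2 on Day 22. Day 22 + 14 = Day 36, which is 36 − 21 = 15 days after the window closes.

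**3. What criterion 9 already catches.** Doses in Cycle 1: 21 × 2 = 42. More than 25% means more than 10.5, so at least 11 missed. An unresolved hold starting with the Day 16 morning dose misses 6 × 2 = 12 by Day 21; from the Day 16 evening dose, 11; from the Day 17 morning dose, 10. A toxicity held from Day 16 or earlier is therefore already a DLT inside the window.

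**4. What stays open (onset day counted as day 1).**
- Grade 4 hematologic, at least 7 days: onset Day 15 gives 7 days by Day 21 (met); onset Day 16 gives 6 (not met, but caught by criterion 9 if held). Left open: onset on about Days 17–21.
- Grade 3 non-hematologic, more than 3 days: onset Day 18 gives 4 days (met); onset Day 19 gives 3 (not met). Left open: about Days 19–21.
- Laboratory, more than 72 hours: onset Day 19 gives 48 hours by Day 21. Left open: about Days 19–21.

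These are calendar days, not shares of DLTs. The flow charts place the first scheduled hematology and chemistry after Day 15 within 3 days before Cycle 2 Day 1, nominally Days 19–22. A laboratory abnormality first seen there will not have more than 72 hours of documented persistence by Day 21.

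**5. Effect of one uncounted DLT on Table 4, cohorts of 3 to 6.**

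| True count | Correct reading | Count as read | Reading obtained |
|---|---|---|---|
| 1/3 | S | 0/3 | E |
| 1/4 | S | 0/4 | E |
| 1/5 | S | 0/5 | E |
| 2/6 | S | 1/6 | E |
| 2/3 | D | 1/3 | S |
| 3/4 | DU | 2/4 | S |
| 3/5 | D | 2/5 | S |
| 4/6 | DU | 3/6 | S |

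Beyond n = 6, each column again has exactly one S-to-E cell: 2/n for n = 7–10 and 3/n for n = 11–14.

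**6. Sensitivity on an assumed input.** Let f be the share of true DLTs still open at Day 21 and read as none. With true rate p, P(E after 3 subjects) = (1 − p(1−f))³. At p = 0.40 (assumed):
- f = 0: 0.60³ = 0.216
- f = 0.1: 0.64³ = 0.262
- f = 0.2: 0.68³ = 0.314
- f = 0.3: 0.72³ = 0.373

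With 6 subjects, where E means at most 1 DLT, the values are 0.233, 0.301, 0.378 and 0.464. The documents give no value for f, so none of these is an estimate for this trial.

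**The case against.** The strongest reply is that section 5.2.2 counts toxicities that occur in Cycle 1. A Grade 3 event starting on Day 20 has occurred in Cycle 1, and only its duration is learned later. Criterion 7, being specific, can be read as qualifying the general window, and section 8.5.1 does not bar a DLT confirmed later. This is a reasonable reading, and the fix adopts it. But the protocol does not state it, and it leaves open what to do while the status is unknown.

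A reader might infer that the protocol forces escalation on Day 21. It does not. Opening a cohort needs both the elapsed 21 days and a joint decision after safety review, and 0/3 permits escalation without compelling it. Dose adjustments in the window are to be discussed with the sponsor (5.2.1.4), unscheduled tests are allowed (7.1), and unresolved drug-related laboratory values are followed (7.1.3.1). All of this allows waiting; none of it requires waiting or gives a scoring rule. The cap on further subjects in section 5.2.1.2 limits accrual and does not address subjects already treated whose status is open.

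Many severe events also qualify with no duration requirement: Grade 4 non-hematologic toxicity, Grade 4 thrombocytopenia, febrile neutropenia, Hy's Law cases, Grade 3–4 laboratory values needing intervention or hospitalization, and toxicity that ends treatment in Cycle 1. That stands, and it is why the open cases are limited to the late, uncomplicated events in step 4 and to criterion 7.

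A reader might also infer that Arm 2 toxicity attributed to pembrolizumab routinely escapes. Section 5.2.3.2 says "Pembrolizumab must be withheld for drug-related toxicities and severe or life-threatening AEs as per" Table 8, and section 5.2.3.1 says "Reduction or holding of one agent and not the other agent is appropriate if, in the opinion of the investigator" links the toxicity clearly to one drug. If only pembrolizumab is held, however, preladenant can start Cycle 2, so criterion 7 need not be engaged. Nor can this arise in Arm 1, so it does not bear on the DL1 decision that opens two cohorts. For that decision there is some reassurance in Table 1: 25 + 19 + 13 + 9 + 27 + 21 = 114 subjects given 25 mg BID, though for 2 to 14 days and in no cancer population.

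**Conclusion.** The point holds and should be fixed. Criterion 7 can never be established inside the stated window, and late-onset duration criteria may not be. The stated rules permit a dose decision in that state and do not say how the subject counts. The consequence is limited to interim escalate and stay decisions, the subjects dosed on them, and the numerator of the DLT rate.

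The size is a possible change of one Table 4 action in the cells listed. The frequency is unknown and probably low, given criterion 9, the criteria with no duration requirement, and the joint review. This rests on calendar arithmetic, on Table 7 holds being applied as written, and on Table 4 as printed.

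Two stronger readings are not supported. A reader might take the chance of landing on an S-to-E cell as the chance of a wrong escalation. At a true rate of 30% that chance is 3 × 0.3 × 0.7² = 44.1% for n = 3, and 41.2%, 36.0% and 32.4% for n = 4, 5 and 6. It is not an error rate, because one of those DLTs must also be unsettled at the decision and be read as none. A reader might also conclude that the final RP2D is compromised. Section 2.1 has it confirmed on all available safety data, including late toxicities, so the documents do not show that.

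**What to change.** In sections 5.2.2 and 8.5.1, state that a toxicity with onset in Cycle 1 counts as a Cycle 1 DLT if it later meets a duration criterion or causes the criterion 7 delay, even when this is confirmed after Day 21.

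In sections 5.2.1.2 and 5.3, define a subject as pending if, when the dose decision is made, either of these holds:

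- (a) a related toxicity with Cycle 1 onset is ongoing at the grade of a duration criterion; or
- (b) an ongoing related toxicity has caused a study drug to be held or is expected to stop Cycle 2 from starting on schedule, or Cycle 2 has not started within its visit window because of related toxicity.

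Tying (b) to the decision rather than to Day 21 matters because Cycle 2 is due on Day 22 with a ±3-day window.

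Then read Table 4 with every pending subject counted as a DLT. Escalate, and open the linked Arm 2 cohort, only if it still reads E. Add subjects at the current dose only if it still reads S or E. Otherwise wait until the status is final. With one pending subject:

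- 0/6 reads 1/6 = E and escalation proceeds.
- 0/3 reads 1/3 = S, so there is no escalation yet, but subjects may be added.
- 1/3 reads 2/3 = D, and 2/4 reads 3/4 = DU, so enrolment at that dose waits.

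The rule should not hold up a de-escalation that the settled count already calls for.

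The cost is wording in four sections and an occasional wait. For onset on Day 21 that is about 3 days for the 3-day and 72-hour criteria (Day 24), about 6 for the 7-day criterion (Day 27), and up to about 15 for criterion 7 (Day 36). In cohorts of 3 to 5, any pending subject is enough to hold an escalation. Table 4 and the planned sample size do not change.
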